**SYNOPSIS: STAGE 2**

Sponsor: Promedior, Inc.
Name of Finished Product: Recombinant human Pentraxin-2; PRM-151
Study Title: A Phase 2, Prospective Study Of PRM-151 In Subjects With Primary Myelofibrosis (PMF), Post-Polycythemia Vera MF (post-PV MF), Or Post-Essential Thrombocythemia MF (post-ET MF)
Study Number: PRM-151G-101
Study Phase: Phase 2
Investigational Product; Dose; and Mode of Administration: PRM-151; 0.3 mg/kg; 3 mg/kg and 10 mg/kg intravenous
Comparator; Dose; and Mode of Administration: Not applicable
Primary Objective(s): 
 
• To determine the effect size of three different doses of PRM-151 on reduction in bone marrow fibrosis by <math>\geq 1</math> grade in intermediate-1, intermediate-2, and high risk subjects with PMF, post-PV MF, or post ET-MF who are anemic or thrombocytopenic and who are ineligible for, intolerant of, or have had an inadequate response to ruxolitinib.
 

Secondary Objective(s): 
 
• To determine if there is a difference in efficacy between the three doses of PRM-151 used in the study
 
• To evaluate the safety and tolerability of three different doses of PRM-151
 
• To assess the duration of effect of three doses of PRM-151 on reduction in bone marrow fibrosis
 
• To assess the effect and duration of effect of three doses of PRM-151 on disease related anemia, thrombocytopenia, and constitutional symptoms
 
• To assess IWG-MRT response (Complete Response, Partial Response, Clinical Improvement), stable and progressive disease in subjects treated with three doses of PRM-151
 

**Exploratory Objectives**

- To measure changes in bone marrow fibrosis by quantitative image analysis and evaluate changes in bone marrow morphology in subjects receiving PRM-151
- To assess the effect of PRM-151 on other disease related parameters, including hematologic abnormalities and spleen size
- To assess the effect of PRM-151 on prognostic factors associated with increased mortality as measured by the DIPSS (Dynamic International Prognostic Scoring System)
- To evaluate the interaction between selected genetic mutations and cytogenetic abnormalities and response to PRM-151
- To explore potential biomarkers of PRM-151 activity in bone marrow samples
- To assess the effect of PRM-151 on bone marrow metabolism by PET imaging (at selected institutions)
- To evaluate the correlation of baseline PTX-2 levels with outcomes
- To evaluate the relationship between bone marrow fibrosis reduction and hematologic improvements in subjects treated with PRM-151
- To measure progression-free and overall survival in subjects receiving PRM-151

**Study Endpoints:****Primary:**

- Bone marrow response rate, defined as the percent of subjects with a reduction in bone marrow fibrosis score by at least one grade according to WHO criteria ([APPENDIX D](#)) at any time during the study as determined by a central adjudication panel of expert hematopathologists, blinded to subject, treatment, and time of biopsy

**Secondary:**

- Comparison of primary and secondary efficacy parameters between doses
- Incidence of adverse events (AEs), serious adverse events (SAEs), and changes in laboratory test results
- Bone marrow improvement:

 
○ Bone marrow response rate at weeks 12, 24, and 36
 
○ Duration of bone marrow response
 
● Hemoglobin improvement
 
	
Baseline Status	Categories of Hemoglobin Improvement
Subjects who are transfusion dependent ( $\geq 2$ units PRBC every 4 weeks for 12 weeks prior to or after C1D1), regardless of baseline hemoglobin level	Percent of subjects with Red cell transfusion independence (no transfusions for $\geq 12$ consecutive weeks) OR 50% reduction in RBC transfusions for $\geq 12$ consecutive weeks
Subjects with baseline hemoglobin $< 100$ g/L AND Not transfusion dependent	Percent of subjects with $\geq 10$ g/L and $\geq 20$ g/L increase in hemoglobin for $\geq 12$ consecutive weeks without transfusions

 
● Platelet improvement:
 
	
Baseline Status	Categories of Platelet Improvement
Subjects who are transfusion dependent ( $\geq 2$ platelet transfusions in any 12 weeks prior to or after C1D1), regardless of baseline platelet level  Platelet transfusion = either 1 unit apheresed (single donor) platelets or 4-8 units pooled random donor platelets	Percent of subjects with: Platelet transfusion independence (no transfusions for $\geq 12$ consecutive weeks)  OR 50% reduction in platelets transfusions for $\geq 12$ consecutive weeks
Subjects with $25 < \text{baseline platelets} < 50 \times 10^9/\text{L}$  AND Not platelet transfusion dependent	Percent of subjects with: Doubling of baseline platelet count for $\geq 12$ consecutive weeks without platelet transfusions  OR Platelet count $> 50 \times 10^9/\text{L}$ for $\geq 12$ consecutive weeks without platelet transfusions
Subjects with baseline platelet count $< 25 \times 10^9/\text{L}$  AND Not platelet transfusion dependent	Percent of subjects with: Doubling of baseline platelet count for $\geq 12$ consecutive weeks without platelet transfusions  OR

	Platelet count > 25 x 10  /L for ≥ 12 consecutive weeks without platelet transfusions

 
Hematologic improvement:
 
	
Baseline Status	Categories of Hematologic Improvement
Subjects with both Hemoglobin < 100 g/L and Platelets < 50 x 10  /L	Percent of subjects who have EITHER Hemoglobin improvement OR Platelet improvement as described above and no worsening of hemoglobin or platelets from baseline
Subjects with only Hemoglobin < 100 g/L	Percent of subjects who have Hemoglobin improvement as described above AND Did not develop platelets < 50 x 10  /L
Subjects with only Platelets < 50 x 10  /L	Percent of subjects who have Platelet improvement as described above AND Did not develop Hemoglobin < 100 g/L or new transfusion dependence

 
Symptom improvement: 
 
Percent of subjects with 25% and 50% reduction in MPN-SAF Total Symptom Score from baseline at Week 36
 
Mean change from baseline at EORTC QLQ-C30 at 36 weeks
 
 
 
Duration of all improvement parameters listed above
 
Percent of subjects with complete response, partial response, clinical improvement, stable disease, and progressive disease according to IWG-MRT criteria (Tefferi 2013, APPENDIX B)
 
 
Exploratory:
 
 
Bone marrow 
 
Percent of subjects with Grade 0-1 bone marrow fibrosis grade at any time during the study and at weeks 12, 24, and 36
 
 
 
	

- Duration of Grade 0-1 bone marrow fibrosis grade
- Mean change from baseline to 12, 24, and 36 weeks in bone marrow fibrosis by quantitative image analysis
- Changes from baseline to weeks 12, 24, and 36 in bone marrow metabolism by FDG or FLT PET scan (where feasible)
- Assessment of changes in bone marrow morphology at 12, 24, and 36 weeks
- Hematologic and other disease related laboratory parameters
  - Mean change from baseline to 36 weeks in: hemoglobin, # RBC units transfused in previous 12 weeks, platelet count, # platelet transfusions in previous 12 weeks, white blood cell count, absolute neutrophil count, reticulocyte count, peripheral blood blast count, and lactic dehydrogenase (LDH)
  - Percent of subjects with increase in Hgb from  $< 100$  g/L to  $> 100$ g/L without transfusions, increase in platelets from  $< 50 \times 10^9$ /L to  $> 100 \times 10^9$ /L, decrease in WBC from  $> 25$  to  $< 25$ , increase in ANC from  $< 1500$  to  $\geq 1500$ , decrease in peripheral blood blasts from  $> 1\%$  to  $< 1\%$ , and disappearance of leukoerythroblastosis, at 36 weeks and for  $\geq 12$  weeks at any time during the study
  - Duration of increase in Hgb from  $< 100$  g/L to  $> 100$  g/L without transfusions, increase in platelets from  $< 50 \times 10^9$ /L to  $> 100 \times 10^9$ /L, decrease in WBC from  $> 25$  to  $< 25$ , increase in ANC from  $< 1500$ , to  $\geq 1500$ , decrease in peripheral blood blasts from  $> 1\%$  to  $< 1\%$ , and disappearance of leukoerythroblastosis
- Spleen improvement:
  - Percent of subjects with 10% and 35% reduction in spleen size from baseline by CT at 36 weeks
  - Duration of 10% and 35% reduction in spleen size from baseline
  - Mean change from baseline in spleen size by CT or MRI at 36 weeks
  - Change in spleen and liver metabolism by FDG or FLT PET scan at 12, 24, and 36 weeks
- DIPSS
  - Percent of subjects with a reduction in DIPSS score and category at week 36
  - Mean change in DIPSS score from baseline to Week 36

- Mutational Status and Cytogenetics
  - Association of baseline mutational status of JAK2V617F, MPLW515, Calreticulin, ASXLI, EZH2, SRSF2, IDH1/2 with selected primary and secondary endpoints
  - Changes in allele burden of JAK2V617F at week 36. Changes in allele burden of MPLW515, Calreticulin, ASXLI, EZH2, SRSF2, IDH1/2 at week 36 will be measured as commercially available assays become available
  - Association of baseline cytogenetic abnormalities and selected primary and secondary endpoints
- Association of baseline PTX-2 levels with selected primary and secondary endpoints
- Evaluation of potential biomarkers of PRM-151 activity in bone marrow biopsies taken at baseline, weeks 12, 24, and 36
- Measurement of progression-free and overall survival

**Stage 2 Study Design:**

This is a randomized, double-blind Phase 2 study to determine the efficacy and safety of three different doses of PRM-151 in subjects with PMF and post ET/PV MF. Subjects will be randomized to one of three doses: 0.3 mg/kg, 3.0 mg/kg or 10 mg/kg of PRM-151. This is the second stage of an adaptive design study as defined in FDA Draft Guidance for Industry: Adaptive Design Clinical Trials for Drugs and Biologics, February 2010. Modifications to dose levels, schedule, and regimen have been made in Stage 2 based on data from Stage 1.

Approximately 84 subjects with intermediate-1, intermediate-2, or high risk MF who meet study eligibility requirements will be enrolled and randomized to treatment with single agent PRM-151 at doses of 0.3, 3, or 10 mg/kg IV on Days 1, 3, and 5 of Cycle 1 and Day 1 of each subsequent 28 day cycle for nine cycles. The randomization will be stratified according to type of subject (subjects with Hgb < 100 g/L and having received  $\geq 2$  units PRBC in the 12 weeks prior to study entry OR subjects with platelet count <  $50 \times 10^9/L$ ) and will ensure that the final study population will include at least 50% of subjects from the second stratum (platelet count <  $50 \times 10^9/L$ ). As outlined in [APPENDIX J](#), all subjects completing 9 cycles of the originally assigned treatment may switch to an open label extension and receive PRM-151 10 mg/kg every 4 weeks.

The first cycle of the open label phase contains a loading dose of 10 mg/kg on days 1, 3, and 5. This will allow for subjects from all three dosing cohorts to receive a loading dose of 10 mg/kg while maintaining the blind. Additionally, subjects who have entered the open label extension study prior to the approval of this amendment may receive a loading dose (10 mg/kg on days 1, 3, and 5), to be administered on their next scheduled cycle after approval of this protocol amendment. This will allow for these subjects to receive any potential pharmacologic benefit of the loading dose.

As of 14-Nov 16, we have blinded safety data, although limited, on 21 subjects receiving a similar 10 mg/kg loading dose in the open label of the PRM-151-202 IPF study after 24 weeks of exposure to PRM-151 or placebo in 2:1 ratio. No incremental risk has been reported in these subjects.

Subjects enrolled in the open-label phase extension protocol of Stage 1 should continue to follow the study procedures outlined in [APPENDIX L](#).

Enrolled subjects will be considered evaluable for response if they are on study drug for at least twelve weeks.

**Study Duration:**

Each subject will participate in the study for approximately 44 weeks. Participation will include a screening evaluation within four weeks prior to the first PRM-151 administration, nine study cycles of four weeks each, and an end of study visit four weeks after the end of the last cycle. After completion of 9 cycles, subjects may continue with PRM-151 dosing in the open label extension in the absence of disease progression or toxicity warranting discontinuation of therapy.

It is estimated that the study will be completed in approximately 18 months.

**Study Inclusion and Exclusion Criteria: Inclusion Criteria:**

1. Subjects must be  $\geq 18$  years of age at the time of signing the Informed Consent Form (ICF);
2. Subjects must voluntarily sign an ICF;
3. Subjects must have a pathologically confirmed diagnosis of PMF as per the WHO diagnostic criteria ([APPENDIX C](#)) or post ET/PV MF;
4. At least Grade 2 marrow fibrosis according to the WHO Grading of Bone Marrow Fibrosis ([APPENDIX D](#));
5. Intermediate -1, intermediate -2, or high risk disease according to the IWG-MRT Dynamic International Prognostic Scoring System ([APPENDIX E](#));
6. A bone marrow biopsy must be performed within four weeks prior to Cycle 1 Day 1 treatment to establish the baseline fibrosis score;
7. Subjects must not be candidates for ruxolitinib based on EITHER:
  - a. Platelet count  $< 50 \times 10^9/L$ , OR
  - b. Hgb  $< 100$  g/L have received  $\geq 2$  units PRBC in the 12 weeks prior to study entry, and be intolerant of or had inadequate response to ruxolitinib;
8. Subjects must have an Eastern Cooperative Oncology Group (ECOG) Performance Status of 0-2 ([APPENDIX F](#));
9. Life expectancy of at least twelve months;
10. At least four weeks must have elapsed between the last dose of any MF-directed drug treatments for myelofibrosis (including investigational therapies) and study enrollment;
11. Recovery to  $\leq$  Grade 1 or baseline of any toxicities due to prior systemic treatments, excluding alopecia;
12. Women of child bearing potential (WCBP), defined as a sexually mature woman not surgically sterilized or not post-menopausal for at least 24 consecutive months if  $\leq 55$  years or 12 months if  $> 55$  years, must have a negative serum pregnancy test within four weeks prior to the first dose of study drug and must agree to use highly effective methods of birth control throughout the study. Highly effective methods of contraception include combined (estrogen and progestogen containing) hormonal contraception associated with inhibition of ovulation by oral, intravaginal, or transdermal administration; progestogen-only hormonal contraception associated with inhibition of ovulation by oral, injectable, or implantable administration; intrauterine device (IUD); intrauterine hormone-releasing system (IUS); bilateral tubal occlusion; partner vasectomy, and total abstinence (only if total abstinence is the preferred method and usual lifestyle of the subject). Adequate contraceptive use should be continued until 28 days after the final dose of the study drug.
13. Ability to adhere to the study visit schedule and all protocol requirements;
14. Must have adequate organ function as demonstrated by the following:
  - ALT (SGPT) and/or AST (SGOT)  $\leq 3$  x upper limit of normal (ULN), or  $\leq 4$  x ULN (if upon judgment of the treating physician, it is believed to be due to extramedullary hematopoiesis [EMH] related to MF);
  - Direct bilirubin  $\leq 1.5$  x ULN; or  $\leq 2$  x ULN (if upon judgment of the treating physician, it is believed to be related to MF);

- Serum creatinine  $\leq 2.5$  x ULN.

**Exclusion Criteria:**

1. White blood cell count  $> 25 \times 10^9/L$  or  $>10\%$  peripheral blood blasts;
2. Other invasive malignancies within the last 3 years, except non-melanoma skin cancer and localized cured prostate and cervical cancer;
3. History of stroke, unstable angina, myocardial infarction, or ventricular arrhythmia requiring medication or mechanical control within the last 6 months;
4. Presence of active serious infection;
5. Any serious, unstable medical or psychiatric condition that would prevent, (as judged by the Investigator) the subject from signing the informed consent form or any condition, including the presence of laboratory abnormalities, which places the subject at unacceptable risk if he/she were to participate in the study or confounds the ability to interpret data from the study;
6. Known history of human immunodeficiency virus (HIV), or known active hepatitis A, B, or C infection;
7. Organ transplant recipients other than bone marrow transplant;
8. Women who are pregnant or lactating.

**Efficacy Assessments:**

Efficacy will be assessed by evaluation of WHO bone marrow fibrosis grade, changes in hemoglobin, platelets, peripheral blood blasts, disease related symptoms, and spleen size.

**Safety Assessments:**

Safety will be evaluated from reported adverse events, scheduled physical examinations, vital signs, and clinical laboratory test results.

A blinded DMC will be established to review safety data from this study, thereby better ensuring the safety of study participants. Consistent with US Food and Drug Administration (FDA) recommendations (FDA Guidance for Industry, Establishment and Operation of Clinical Trial Data Monitoring Committees, 2006), the DMC will be constituted of independent clinicians expert in the field of MF and clinical research. A formal charter will be established for the conduct of the DMC.

- The committee is planned to review the safety data in a blinded manner, but a procedure will be in place to allow the committee an immediate unblinding of either specific cases or of the whole study in case of detection of a potential safety signal necessitating an unblinded review of some (or all) subjects.

**Statistical Methods:****General considerations:**

Continuous variables will be summarized by dose group with descriptive statistics (e.g., number of observations, number of missing observations, mean, standard deviation [SD], median, interquartile range, maximum, and minimum). Categorical variables will be tabulated by frequency of subjects per dose group, and percentages will be calculated using the number of available observations as the denominator (i.e. excluding missing values).

**Determination of Sample Size**

The chosen sample size of 72 subjects (i.e. 24 subjects per dose arm) is deemed sufficient to provide adequate precision to the estimation of the response rate in each treatment arm. The trial will enroll 84 subjects to allow for a discontinuation rate of 15%.

Considerations on the precision of estimate and the power for comparisons planned as secondary analyses are provided in the body of the protocol.

**Randomization and Stratification**

This study is randomized with a 1:1:1 randomization ratio. A central randomization system will be used. The randomization will be stratified according to the subjects' baseline haematologic status: baseline anemia alone or baseline thrombocytopenia or baseline anemia associated with baseline thrombocytopenia. The randomization system will also ensure that at least 50% of the subjects in the final study population will have baseline thrombocytopenia.

**Missing values:**

All available efficacy and safety data will be included in data listings and tabulations.

For the primary efficacy criterion, subjects with a reduction in bone marrow fibrosis score by at least one grade according to WHO criteria (central adjudication) at any post baseline visit will be considered as responders. Subjects without any central assessment of bone marrow fibrosis will be considered as non-responders. In addition, subjects who discontinue due to toxicity prior to completion of one cycle of study drug will be also considered non-responders for the efficacy analyses.

All other analyses will be based on observed data only; no missing data will be imputed.

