### **10.3.2 Descriptive statistics**

Quantitative variables will be described by treatment group using the following statistics: number of available data, number of missing values, mean, standard deviation, median, Q1, Q3, minimum and maximum values. When relevant, confidence intervals will also be computed.

Qualitative variables will be described by treatment group using number of available data, number of missing values, frequency counts for each category and corresponding percentage. Percentages will be calculated using the number of available data as the denominator (i.e. not including missing values). When relevant, confidence intervals will also be computed.

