### **10.3.4. Missing, Unused, and Spurious Data**

All available efficacy and safety data will be included in data listings and tabulations. For the primary efficacy criterion analysis, subjects with a reduction in bone marrow fibrosis score by at least one grade according to WHO criteria (central adjudication) at any post baseline visit will be considered as responders. Subjects without any central assessment of bone marrow fibrosis will be considered as non-responders. In addition, subjects who discontinue due to toxicity prior to completion of one cycle of study drug will also be considered non-responders for the efficacy analyses.

Except for the imputation of missing values for the analysis of the primary criterion as described above, all other analyses will be based on observed data only; no missing data will be imputed.

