4.9 MISSING DATA

All available efficacy and safety data will be included in data listings and tabulations. No imputation of values for missing data will be performed. Subjects with missing post baseline response data, for any reason, will be counted as non responders.

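### For Stage 2 visit-specific secondary response rates, the protocol drops missing subjects from the denominator and SAP 4.9 counts them as non-responders; at the planned 15% loss the rules differ by about 6.5 points near a 46% rate and by under 1 point at 5%.

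*Protocol*

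**What the plan says.** **Protocol.** The synopsis (Missing values) sets a non-responder rule for the primary criterion and then states "All other analyses will be based on observed data only; no missing data will be imputed". Section 10.3.4 repeats this: "all other analyses will be based on observed data only; no missing data will be imputed". The denominator follows the same line, in the synopsis ("percentages will be calculated using the number of available observations as the denominator (i.e. excluding missing values") and in 10.3.2 ("Percentages will be calculated using the number of available data as the denominator (i.e. not including missing values"). One exception reaches past the primary endpoint: "subjects who discontinue due to toxicity prior to completion of one cycle of study drug will also be considered non-responders for the efficacy analyses" (10.3.4).

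**SAP.** Section 4.9 holds two sentences that pull apart: "No imputation of values for missing data will be performed" and then "Subjects with missing post baseline response data, for any reason, will be counted as non responders". The second is not limited to the primary endpoint and names no visit. Section 4.1.1 makes all treated subjects the primary efficacy population. Appendix 3 reproduces the protocol synopsis, including its observed-data rule, without marking it as superseded.

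**Endpoints affected.** Protocol 3.2 lists marrow response at Weeks 12, 24 and 36 and the share of subjects with 25% and 50% symptom score reductions at Week 36. SAP 2.2.2 keeps marrow response by visit and the 50% symptom response over time. Protocol 10.6.1.3.4 plans pairwise dose comparisons of all secondary endpoints at two-sided 0.05.

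**The concern.** The same subject can be out of the denominator under one document and a failure under the other. Under the observed-only rule, a Week 36 rate describes those who stayed. Reasons for removal in protocol 7.14 include intolerable adverse events and developing an exclusion criterion, so loss may well be related to outcome. If those who leave respond less often, the observed-only rate is too high for the treated population, and an arm that loses more non-responders gains in the pairwise tests.

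The protocol's rule also makes the Week 36 mean change in QLQ-C30 a completer mean, although the questionnaire is given every cycle (protocol 8.4 and 8.5). SAP 4.9 does not alter that, because its non-responder sentence concerns response data only.

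**Working it through.** **Inputs from the documents.** 84 enrolled, 72 evaluable, 24 evaluable per arm, 15% discontinuation; assumed response of 5% (0.3 mg/kg) and 46% (10 mg/kg) (all protocol 10.1). Those two rates are any-time primary-endpoint assumptions. No secondary rate is given, so they serve here only as stand-ins.

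**Plan's own figure.** 72/(1 − 0.15) = 84.7, so 85; 72 × 1.15 = 82.8, so 83. The stated 84 agrees to within two subjects. It implies 12/84 = 14.3% loss, or 4 of 28 per arm.

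**Formula.** With n treated, m missing and x observed responders, the observed-only rate is x/(n − m) and the non-responder rate is x/n. Their gap is [x/(n − m)] × (m/n), that is, the observed-only rate times the share missing.

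**At the planned loss (n = 28, m = 4, no responder lost).**

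| Observed responders | Observed-only | Missing = non-response | Gap |
|---|---|---|---|
| 11 | 11/24 = 45.8% | 11/28 = 39.3% | 6.5 points |
| 1 | 1/24 = 4.2% | 1/28 = 3.6% | 0.6 points |

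Using the rounded planning values instead, 0.46 × 0.15 = 6.9 points and 0.05 × 0.15 = 0.75 points. The contrast between doses moves as well: 46 − 5 = 41.0 points observed-only, against 0.85 × 41 = 34.85 points if both arms lose 15%.

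**What a 16-point gap needs (assumption).** Keep 11 responders and lose 8 of 28 (28.6%), all non-responders: 11/20 = 55.0% against 39.3%, a gap of 15.7 points. If the observed-only rate is instead held at 46% or 40%, the share missing must be 0.16/0.46 = 35% or 0.16/0.40 = 40%.

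**Effect on a test (hypothetical counts, unstratified chi-square without continuity correction).** 10/28 against 4/28 gives p = 0.064. If four non-responders are missing in the first arm only, observed-only gives 10/24 against 4/28, p = 0.026. The choice of denominator alone moves the result across 0.05.

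**The case against.** The strongest reply is that the SAP already settles this. Protocol 10.3.1 leaves detail to the SAP, SAP 4.1.1 takes all treated subjects, SAP 4.9 counts missing response as failure, and Appendix 3 is only a copy of the protocol synopsis. Read visit by visit, that is close to the rule wanted here. But 4.9 does not say that it applies visit by visit. SAP 4.4.1, for the primary endpoint, speaks of subjects with no readable post-baseline biopsy at all. If 4.9 means the same, someone with a Week 12 biopsy and none at Week 36 is not covered, and the gap produced by 4.9 shrinks while the Week 36 denominator stays undefined. This SAP was also signed after the Stage 2 primary lock (SAP section 1). The earlier Stage 2 SAP is not available, so a change of denominator between the two reports cannot be ruled out.

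Other objections stand and limit the point:

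- Upward bias is conditional. If missingness is unrelated to response, the observed-only rate is unbiased and the non-responder rate is too low.
- A reader might infer an inconsistency with the primary analysis, where unassessed subjects are non-responders. The contrast is weak, because the protocol's Full Analysis Set (10.5.1) already excludes most subjects without a post-baseline marrow assessment.
- A reader might extend the point to every non-primary endpoint. Early-toxicity dropouts are already failures, hemoglobin and platelet improvement are sustained 12-week criteria, and marrow response duration is censored.
- A mixed model for hemoglobin or symptom score change is not called for. Hemoglobin change is exploratory in both documents; symptom score change is exploratory in the SAP, while the protocol uses responder percentages. Exploratory endpoints are only described. The SAP also lists QLQ-C30 change as exploratory, but the protocol makes it secondary and formally compared.
- SAP 4.4.2 does not itself restate pairwise tests for the Stage 2 secondary endpoints; they come from the protocol.

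**Conclusion.** The conflict is real for the Stage 2 visit-specific secondary responder endpoints: marrow response at Weeks 12, 24 and 36, and symptom score response. With the planned loss and no responders among those lost, it is worth about 6.5 points in an arm near 46% and under 1 point in an arm near 5%. Both figures borrow primary-endpoint rates.

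A reader might infer a general discrepancy of 6 to 16 points. The documents do not support it: 15% is the only loss they state, the upper end needs about 30% missing with every lost subject a non-responder, and the range fails altogether for a low-response arm. Nor do they show that the observed-only rate is biased; that depends on dropouts responding less often, which is plausible but assumed. The primary comparison with the 10% threshold is not touched. The point should be corrected because the protocol's rule feeds formal comparisons and can change a reported secondary result.

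**What to change.** - State one rule in the protocol synopsis, protocol 10.3.2 and 10.3.4, and SAP 4.9: each responder endpoint uses all treated subjects as denominator, and a missing value at the analysed visit counts as non-response. Give observed-case rates as supportive.
- In SAP 4.9, define missing by visit and limit the no-imputation sentence to what it is meant to cover. Mark the rule reprinted in Appendix 3 as superseded.
- Declare in the study report any change from the earlier Stage 2 analysis.
- For QLQ-C30 change at Week 36, replace the completer mean with a mixed model for repeated measures on all post-baseline visits, with baseline value, visit, dose, dose-by-visit and stratum.

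The cost is wording in two documents and a little standard programming. The downside is that reported secondary response rates become lower, and too low if dropouts respond as often as those who stay; the supportive observed-case rates let the reader see that.
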